7. TREATMENTS

The following is a list of the study treatment abbreviations and ordering that will be used in the TFLs.

Study Treatment Name	Treatment Abbreviation on TFL	Treatment Order on TFL	Cohort
Pooled Placebo TID	Pooled Placebo	1	1-5
30 mg UV-4B TID	UV-4B 30 mg	2	1
75 mg UV-4B TID	UV-4B 75 mg	3	2
150 mg UV-4B TID	UV-4B 150 mg	4	3
XX mg UV-4B TID	UV-4B XX mg	5	4
XX mg UV-B TID	UV-4B XX mg	6	5

8. SAMPLE SIZE JUSTIFICATION

The sample size chosen for this study is not based on statistical considerations. The number of subjects within each dose group was chosen based on historical experience with safety and tolerance trials. The sample size falls within the range of those used in other studies of this nature.

9. DEFINITION OF ANALYSIS POPULATIONS

The **All Subjects Population** will consist of any subjects who signed informed consent (excluding screen failures), and had study data recorded on the database as per the protocol.

The **Intent to Treat Population** (ITT Population) will consist of all randomized subjects in the groups to which they are randomly assigned, regardless of their adherence to the inclusion-exclusion criteria, regardless of the treatment they actually received, and regardless of subsequent withdrawal from treatment or deviation from the protocol.

The **Safety Population** will consist of all subjects who received at least 1 dose of study drug (UV-4B, placebo). The safety population will be analyzed according to the treatment and dose level into which the subjects are enrolled.

The **PK Population** will be defined as all subjects who received at least 1 dose of study drug (UV-4B) and have evaluable PK data, and complete scheduled post-dose PK measurements without protocol deviations, violations, or events thought to significantly affect the PK of the drug. Examples of significant protocol deviations, violations, or events include, but may not be limited to, vomiting occurring within 30 minutes following oral dosing, sample processing errors that lead to inaccurate bioanalytical results, and/or inaccurate dosing on the day of PK sampling. In the case of a significant protocol deviation, PK data collected during the affected treatment period will be excluded from summary statistics, but will be included in individual subject listings.

All protocol deviations that occur during the study will be considered for their severity/impact and the assignments of subjects to analysis populations will be finalized prior to database lock and unblinding. Details of subject assignment to the analysis populations will be listed.

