	
and Drug Administration (FDA), for review. The study will be paused during FDA review and dose escalation will only proceed upon approval by the FDA.
 
A protocol amendment for further dose escalations (Cohorts 4 and 5), if appropriate, will be submitted to DMID, the SMC and the FDA for review after Cohort 3. In accordance with DMID stated policy, Emergent Product Development Gaithersburg, Inc. (Emergent) will allow for a 30-day FDA review of any such protocol amendment. Safety assessments will include telemetry, 12-lead electrocardiogram (ECG) measurements, vital signs, physical examinations, clinical laboratory assessments (hematology, serum chemistry, coagulation, urinalysis, vomitus occult blood and fecal occult blood), and adverse events (AEs). Blood samples will be collected for pharmacokinetics at multiple time points until discharge. Plasma will be tested to determine the following parameters for UV-4B in subjects:
 
UV-4 plasma concentrations and pharmacokinetic (PK) parameters determined on day 1 (after first dose up to second dose) and after last dose on Day 7
 
Maximum plasma concentration [C_{max}]
 
Time to reach maximum plasma concentration [t_{max}]
 
Area under the plasma concentration curve from time zero extrapolated to last quantifiable concentration [$AUC_{(0\text{-}last})}$] (after first dose report $AUC_{(0\text{-}8)}$),
 
Total daily exposure ($AUC_{(0\text{-}24)}$)
 
AUC from time zero extrapolated to infinity [$AUC_{(0\text{-}inf)}$] (Day 7 only),
 
Systemic clearance [CL/F]
 
Volume of distribution [V_z/F],
 
Terminal half-life [$t_{1/2}$] (after last dose),
 
Accumulation ratio as defined by $AUC_{(0\text{-}8)}$ after the last dose divided by $AUC_{(0\text{-}8)}$ after the first dose,
 
The results of these preliminary safety and PK results will be listed and summarized to assist in future dose calculations.

Estimated Time to Complete Enrollment:	Approximately 10 months

Schematic of Study Design

Continuation of study will be upon FDA approval only

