11.4.2 Randomization and Stratification

Subject data will be analyzed according to treatment administered, as is standard for early clinical studies, due to the focus on safety and PK data. No stratification is planned for this study.

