11.4.6 Pharmacokinetics

Pharmacokinetic parameters will be calculated by noncompartmental analysis using WinNonlin Professional® Version 5.2 or higher. All calculations for final plasma parameter analysis will be based on nominal sampling times. PK analysis will be performed at the completion of each cohort. The following PK parameters will be estimated:

- C_{\max}
- t_{\max}
- $AUC_{(0-\text{last})}$
- $AUC_{(0-8)}$
- $(AUC_{(0-24)})$
- $AUC_{(0-\infty)}$
- CL/F
- Vz/F
- $t_{1/2}$
- Accumulation ratio as defined by $AUC_{(0-8)}$ after the last dose divided by $AUC_{(0-8)}$ after the first dose

Plasma concentrations and plasma PK parameters will be summarized by cohort. PK parameters will also be presented in graphs as detailed in the SAP.

Dose proportionality of C_{\max} , $AUC_{(0-\text{last})}$, and $AUC_{(0-\infty)}$ will be assessed graphically and statistically using the power model approach with the logarithm of PK parameters $AUC_{(0-\infty)}$ and C_{\max} as the dependent variables and the logarithm of the dose as the independent variable: $([AUC_{(0-\infty)}, AUC_{(0-\text{last})}, \text{ or } C_{\max}] = \alpha * \text{dose}^{\beta})$.

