4. INTRODUCTION

This SAP has been developed after review of the clinical study protocol (Protocol Amendment 3, dated 10 January 2017).

This SAP describes the planned analysis of the safety, tolerability, and pharmacokinetic (PK) data from this study. A detailed description of the planned TFLs to be presented in the Clinical Study Report (CSR) is provided in the accompanying TFL shell document.

The intent of this document is to provide guidance for the statistical analyses of PK data. In general, the analyses are based on information from the protocol, unless they have been modified by agreement between Emergent Product Development Gaithersburg, Inc and [REDACTED] Early Clinical (EC) Biometrics. A limited amount of information concerning this study (eg, objectives, study design) is given to help the reader's interpretation. This SAP must be finalized prior to the lock of the clinical database for this study. When the SAP and TFL shells are agreed upon and finalized, they will serve as the template for this study's analysis presentation in the CSR.

The principal features of the proposed statistical analysis for this study were specified in the protocol before study initiation. This SAP provides more detail on the statistical considerations identified in the protocol; where considerations are different from the protocol, they will be so identified. If additional analyses are required to supplement the planned analyses described in this SAP, they may be performed and will be identified in the CSR. Any substantial deviations from this SAP will be agreed upon between Emergent Product Development Gaithersburg, Inc and [REDACTED] EC Biometrics and identified in the CSR.

This SAP is written with consideration of the recommendations outlined in the International Conference on Harmonisation (ICH) E9 guideline entitled, "Guidance for Industry: Statistical Principles for Clinical Trials" and the ICH E3 guideline entitled, "Guidance for Industry: Structure and Content of Clinical Study Reports."^{1,2}

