10.5 Pharmacokinetic Assessment

10.5.1 Pharmacokinetic Analysis

Where possible, the following PK parameters will be determined from UV-4 plasma concentrations on Day 1 and Day 7 and using non-compartmental methods³ performed in Phoenix WinNonlin (Certara USA, Inc., Version 6.4 or higher):

Parameter	Definition
C _{max}	Observed maximum plasma concentration
t _{max}	Time to reach maximum plasma concentration
AUC _(0-last)	Area under the concentration-time curve from time zero to time of last quantifiable concentration after the final dose on Day 7, calculated using the linear trapezoidal rule for increasing concentrations and the logarithmic rule for decreasing concentrations

$AUC_{(0-8)}$	Area under the concentration-time curve from time zero to 8 hours after first daily dose on Day 1 and after the final dose on Day 7, calculated using the linear trapezoidal rule for increasing concentrations and the logarithmic rule for decreasing concentrations
$AUC_{(0-24)}$	Total daily exposure at steady state, calculated as $AUC_{(0-8h)} \times 3$ (Day 7 last dose only)
CL/F	Apparent systemic clearance at steady state (Day 7 only), calculated as dose divided by $AUC_{(0-8)}$
V_z/F	Apparent volume of distribution during the terminal phase, calculated as $CL/F / \lambda_z$ after multiple doses (Day 7 only)
$t_{1/2}$	Apparent terminal half-life (Day 7 only), calculated as $\ln(2)/\lambda_z$
AR	Accumulation ratio, calculated as $AUC_{(0-8)}$ after last dose/ $AUC_{(0-8)}$ after first dose

Additional PK parameters may be determined where appropriate.

Pharmacokinetic analysis will be carried out using actual sampling times.

Concentrations for PK analyses will be used as supplied by the analytical laboratory. The units of concentration and resulting PK parameters, with amount or concentration in the unit, will be presented as they are received from the analytical laboratory.

If multiple peaks occur, the highest postdose concentration will be reported as C_{max} . In the case that multiple peaks are of equal magnitude, the earliest t_{max} will be reported.

10.5.2 Criteria for Handling Concentrations Below the Limit of Quantification in Pharmacokinetic Analysis

- Concentration values that are below the level of quantification (BLQ) will be set to zero, with defined exceptions as follows;

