12. CHANGES FROM THE PROTOCOL SPECIFIED STATISTICAL ANALYSES

There were no changes from the protocol specified statistical analyses.

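### SAP Section 9 groups safety data by enrolled treatment where the protocol requires treatment administered, and SAP Section 12 declares no changes although this and three other analysis items differ

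*SAP*

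**What the plan says.** **Grouping.** Protocol 11.4.2 states: "Subject data will be analyzed according to treatment administered, as is standard for early clinical studies". It gives the focus on safety and PK as the reason. SAP Section 9 states for the Safety Population: "The safety population will be analyzed according to the treatment and dose level into which the subjects are enrolled". The same SAP section defines a separate ITT Population by random assignment, "regardless of the treatment they actually received".

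**Declaration of changes.** SAP Section 4 allows departures from the protocol but promises that "where considerations are different from the protocol, they will be so identified". SAP Section 12 then says: "There were no changes from the protocol specified statistical analyses".

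**PK times.** Protocol 11.4.6: "All calculations for final plasma parameter analysis will be based on nominal sampling times". SAP 10.5.1: "Pharmacokinetic analysis will be carried out using actual sampling times".

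**AUC(0-inf).** The Protocol Summary lists "AUC from time zero extrapolated to infinity" for Day 7. Protocol 3.2.2 makes it a secondary outcome and Protocol 11.4.6 makes it a power-model variable. It is missing from the SAP's outcome list (Section 5), parameter table (10.5.1) and dose-proportionality set (10.6.3).

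**Laboratory baseline.** Protocol 8.2.1 takes the Day -1 results as baseline for chemistry, hematology and urinalysis. Protocol 7.2.1 also calls the Day -1 coagulation draw baseline. SAP 10.1 and 10.7.4 use the last value before the first dose.

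**Replacement of subjects.** SAP Section 6 rules out replacement after randomization, then has the SMC decide after a halt whether any subjects need replacing. Protocol 5.3.3 says that withdrawn subjects are not replaced.

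**The concern.** Adverse events and laboratory changes are the primary outcomes. Safety is descriptive only (SAP 10.7.8), so the by-treatment summary tables are the main safety result. If a subject receives the wrong product or dose level, the SAP rule puts that subject's events under a treatment the subject did not take. With six subjects per dose, one such subject can change the comparison visibly.

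SAP Section 12 is where a reader looks for departures from the protocol. Anyone relying on it would not learn that a named secondary outcome was dropped, that the PK time basis was changed, or that the baseline for a primary outcome was moved for some analytes.

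**Working it through.** The plan states no figure that bears on this point. The check is a comparison of texts, followed by simple proportions to show the size of the grouping effect.

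**1. Does the SAP contain an as-treated safety set?** SAP Section 9 defines four populations. ITT is by assignment. Safety is by the treatment and dose level enrolled into. All Subjects carries no treatment rule. The PK Population requires receipt of UV-4B but is not a safety set. No sentence in the SAP restores treatment administered for the safety tables.

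**2. Is SAP Section 12 accurate if nobody is mis-dosed?**

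| Item | Protocol | SAP |
|---|---|---|
| PK times | Nominal (11.4.6) | Actual (10.5.1) |
| AUC(0-inf) | Parameter, secondary outcome, power-model variable (Summary, 3.2.2, 11.4.6) | Absent (5, 10.5.1, 10.6.3) |
| Dose-proportionality set | Cmax, AUC(0-last), AUC(0-inf) (11.4.6) | Cmax, AUC(0-last), AUC(0-8) (10.6.3) |
| Laboratory baseline | Day -1 (8.2.1; 7.2.1 for coagulation) | Last pre-dose value (10.1, 10.7.4) |

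The two AUC rows are one change. The baseline row has a practical effect because platelets, AST, ALT, INR, PT and aPTT are drawn again before the first dose on Day 1 (Protocol 8.2.1, Table 5 note b, Appendix IV note g). For those six analytes the SAP baseline is the Day 1 value. Three analysis items therefore differ without being declared, in addition to the grouping rule.

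**3. Size of the grouping effect.** Inputs: 6 UV-4B and 2 placebo subjects per cohort (Protocol 11.2), with placebo pooled across cohorts (Protocol 11.4.5). Pooled placebo is P = 2 × 3 = 6 after three cohorts, or 2 × 5 = 10 after five.

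Assume one placebo-assigned subject receives UV-4B and has the event, *a* of the six assigned to that dose have it, and no other placebo subject does:

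- as treated: (a + 1)/7 against 0/(P − 1)
- as the SAP would tabulate it: a/6 against 1/P

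| Case | As treated | As tabulated | Difference in points |
|---|---|---|---|
| a = 2, three cohorts | 3/7 (42.9%) v 0/5 | 2/6 (33.3%) v 1/6 (16.7%) | 42.9 becomes 16.7 |
| a = 2, five cohorts | 3/7 (42.9%) v 0/9 | 2/6 (33.3%) v 1/10 (10.0%) | 42.9 becomes 23.3 |
| a = 0, three cohorts | 1/7 (14.3%) v 0/5 | 0/6 v 1/6 (16.7%) | +14.3 becomes −16.7 |
| a = 0, five cohorts | 1/7 (14.3%) v 0/9 | 0/6 v 1/10 (10.0%) | +14.3 becomes −10.0 |

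The opposite error is milder. If a UV-4B-assigned subject receives placebo and has no event, and two others at that dose do, 2/5 (40.0%) v 0/7 after three cohorts is tabulated as 2/6 (33.3%) v 0/6. The difference falls from 40.0 to 33.3 points.

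If nobody receives the wrong product or dose level, the two rules give identical tables. Missed or partial doses of the correct product do not separate them.

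**The case against.** **Enrolled may be loose wording.** The sentence does not say randomized or assigned, membership of the Safety Population requires at least one dose, and Protocol 5.3.1 has subjects dosed immediately after a number is assigned. The authors may have meant treatment received. That is possible. But the same section shows that they knew the difference between assigned and received, and they wrote no as-treated rule for safety. As it stands, the text conflicts with Protocol 11.4.2.

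**The effect is hypothetical.** An unblinded pharmacist assigns numbers, trained clinic staff give the doses, and cohorts run one dose level at a time, so a product error may be unlikely. The event counts above are illustrative and the larger effects come from the less favourable direction. Listings of AEs and deviations would reveal the case. All of this stands and limits the weight of the point, but it does not make the tables follow the protocol. The protocol also gives no rule for a subject exposed to more than one product, so repeating its wording would not be enough.

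**The laboratory baseline is less clear-cut.** The protocol's Day -1 statements sit in procedure sections linked to eligibility, and the sentence in 8.2.1 does not name coagulation. Protocol 9.2.1 treats conditions present up to the first dose as pre-existing, and Protocol 7.3.1 lists Day 1 chemistry, hematology and coagulation after dosing. In reply, 9.2.1 concerns AE reporting only, and 7.3.1 does not displace the pre-dose Day 1 draw stated in 8.2.1, Table 5 and Appendix IV. The conflict is explicit for platelets, AST and ALT. For INR, PT and aPTT it rests on Protocol 7.2.1.

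**The SAP permits additional PK parameters and agreed changes.** Neither provision restores a named outcome or excuses silence in Section 12.

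**Three items may be too few.** The SAP also adds the All Subjects and ITT populations, and it uses unscheduled values in baselines and the ECG outlier analysis, where Protocol 11.4.3 provides only for listing them. This lengthens the list for Section 12 and does not weaken the point.

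**Conclusion.** The concern holds and should be fixed. SAP Section 9 replaces the protocol's as-treated rule for the primary safety tables, and SAP Section 12 denies any change.

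The grouping conflict has a numerical effect only after a product or dose-level error, whose probability the documents do not give. In the illustrations, one such subject with an event cuts a difference of 42.9 points to 16.7 (three cohorts) or 23.3 (five cohorts), or reverses the direction if it is the only event. These figures assume the subject counts wholly under the product received.

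The inaccuracy of Section 12 needs no such assumption. The PK-time, AUC and laboratory-baseline changes apply in every case. Each may be a reasonable choice; the fault is that none is declared. The statements on replacing subjects are a separate inconsistency of study conduct.

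**What to change.** Before database lock and unblinding:

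- **SAP Section 9:** state that the Safety Population is analysed by the treatment actually administered. Add a pre-specified rule, chosen by the sponsor, for subjects exposed to more than one product or dose level.
- **SAP Section 12:** replace the statement of no changes with a list giving the PK-time change, the removal of AUC(0-inf) and addition of AUC(0-8), and the laboratory-baseline change, each with its reason. Add the extra populations and the use of unscheduled values so that the list is complete.
- **SAP Section 6:** reconcile its two statements on replacing subjects with each other and with Protocol 5.3.3.

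The cost is SAP wording only, with no new data. The Section 9 change restores the protocol's own rule; only the mixed-exposure rule is new.

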5.3.3 Reasons for Withdrawal

Subjects will be informed that they have the right to withdraw from the study at any time for any reason without prejudice to their medical care. Data collected for withdrawn subjects will be evaluated for safety and PK.

Subjects may be withdrawn from the study for any of the following reasons:

1. Withdraws consent;
2. Noncompliance with study procedures and/or requirements;
3. Death;
4. Pregnancy;
5. In the opinion of the site PI and Sponsor, does not meet eligibility criteria upon admission to unit;
6. Has met Halting Criteria (see [Section 9.7](#))
7. Administrative reasons/other.

In all cases of withdrawal, the reason for withdrawal will be recorded. Subjects who are withdrawn from the study will be asked to complete all Day 15 ± 1 safety assessments including follow-up of any AEs prior to termination from the study. Once randomized, subjects who withdraw from the study for any reason will not be replaced.

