9.7 Individual Dose Limiting Toxicity

- Any single grade 3 AE or Lab abnormality
- Fecal occult blood remains positive for 3 consecutive stool samples, hemorrhoids are excluded
- Evidence of frank hematemesis or hematochezia/melena of any duration
- Any clinical signs or symptoms the PI has determined is unsafe to administer IP

If an individual subject in a cohort reaches dose limit toxicity as determined by any of the above criteria, the subject will not receive any additional doses, and will be withdrawn from the study. All subjects withdrawn from the study will undergo routine follow up safety monitoring.

9.8 Safety Oversight (Safety Review Committee, Independent Safety Monitor plus Safety Monitoring Committee)

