11.4 Final Analysis Plan

11.4.1 Populations for Analysis

The safety population will be defined as all subjects who receive study product or placebo.

The PK population will consist of all subjects who receive study product, and have measurable values, and complete scheduled post-dose PK measurements without protocol

deviations, violations, or events thought to significantly affect the PK of the drug. In the case of a significant protocol deviation, PK data collected during the affected treatment period will be excluded from the analysis. Examples of significant protocol deviations or events include, but are not be limited to: vomiting following oral dosing occurring within 30 minutes, sample processing errors that lead to inaccurate bioanalytical results, and/or inaccurate dosing on the day of PK sampling.

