10. STATISTICAL METHODOLOGY

10.1 General

Data listings and summary statistics and statistical analyses will be performed for subjects included in the relevant analysis populations (All Subjects/ITT/Safety/PK).

For continuous data, summary statistics will include number of observations (n), the arithmetic mean, arithmetic standard deviation (SD), median, minimum (Min), and maximum (Max); for log-normal data (eg, the PK parameters: AUCs and C_{max}) the geometric mean and geometric coefficient of variation expressed as a percentage (CV%) will also be presented. For categorical data, frequency counts and percentages will be presented. For the calculation of summary statistics and statistical analysis, unrounded data will be used.

Baseline is defined as the last value for each assessment prior to the subject's first dose, including unscheduled values. Mean change from baseline is the mean of all individual subjects' change from baseline values. Each individual change from baseline will be calculated by subtracting the individual

subject's baseline value from the value at the timepoint. The individual subject's change from baseline values will be used to calculate the mean change from baseline using appropriate SAS[®] procedures such as Proc Univariate.

Missing values will not be imputed.

Data analysis will be performed using SAS[®] Version 9.3.

Analysis Data Model (ADaM) datasets will be prepared using Clinical Data Interchange Standards Consortium (CDISC) Analysis Data Model Version 2.1, and CDISC ADaM Implementation Guide Version 1.1. Pinnacle 21 Version 2.1.0 or higher will be utilized to ensure compliance with CDISC standards.

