10.5.4 Calculation of AUC

- The minimum requirement for the calculation of AUC will be the inclusion of at least 3 consecutive plasma concentrations above the lower limit of quantification (LLOQ), with at least one of these concentrations following C_{max} .

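### As worded, the PK population drops a subject withdrawn before the final Day 7 dose from the Day 1 and trough summaries, and no passage reconciles this with the protocol's withdrawal section

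*SAP*

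**What the plan says.** Protocol 11.4.1 states: "The PK population will consist of all subjects who receive study product, and have measurable values, and complete scheduled post-dose PK measurements". SAP section 9 repeats the condition, asking for at least one UV-4B dose, evaluable PK data, "and complete scheduled post-dose PK measurements without protocol deviations, violations, or events thought to significantly affect the PK of the drug". The same SAP section says that subjects are assigned to populations before database lock and unblinding. Its only partial-exclusion rule removes data from the affected treatment period, and the trigger is a significant protocol deviation.

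SAP 10.1 supplies the link to the tables: "summary statistics and statistical analyses will be performed for subjects included in the relevant analysis populations".

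On withdrawal, protocol 5.3.3 says: "Data collected for withdrawn subjects will be evaluated for safety and PK". It adds: "Once randomized, subjects who withdraw from the study for any reason will not be replaced". Protocol 9.7 gives one route to early withdrawal: once an individual toxicity criterion is met, "the subject will not receive any additional doses, and will be withdrawn from the study".

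The detailed PK sections of the SAP work at the level of the profile or parameter. Section 10.5.1 says: "Where possible, the following PK parameters will be determined from UV-4 plasma concentrations on Day 1 and Day 7". Section 10.5.4 says: "The minimum requirement for the calculation of AUC will be the inclusion of at least 3 consecutive plasma concentrations". Section 10.6.2 sets missing or uncalculated parameters to missing, and section 10.6.3 calls for by-cohort summaries of all concentrations and derived parameters.

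**The concern.** The completion condition is joined to the others by a plain conjunction and applies to the subject, not to a day or a profile. A subject withdrawn on Day 3, say, has not completed the schedule. Followed literally, that subject is outside the PK population, and SAP 10.1 then takes the subject out of every PK summary, including those for which the data are complete and valid.

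What is lost is usable Day 1 and trough data in cohorts of only six active subjects, with no replacement of withdrawn subjects. Timing adds to the problem. PK is analysed after each cohort (protocol 11.4.6, SAP 11), while population membership is settled only before database lock. If the rule stays ambiguous, someone will have to interpret it when the concentrations already exist.

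**Working it through.** **Inputs**
- Active subjects per cohort: 6 (protocol 11.2).
- PK samples: Day 1, one pre-dose and ten post-dose; Days 2 to 6, one trough a day; final Day 7 dose, one pre-dose and thirteen post-dose; Day 10, one (SAP 6, protocol 7.3 and Appendix IV).
- Stated total: 31 samples (protocol Table 6).

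**Step 1. Reproduce the stated schedule.** Day 1: 1 + 10 = 11. Troughs: 5. Final-dose profile: 1 + 13 = 14. Day 10: 1. Total: 11 + 5 + 14 + 1 = 31, which matches Table 6.

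**Step 2. What a withdrawn subject has already given.** With only Day 1 complete: 11/31 = 35%. Withdrawn just before the final-dose profile, with all troughs taken: (11 + 5)/31 = 16/31 = 52%. On the literal rule, none of this enters the summaries.

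**Step 3. Effect on precision.** At a fixed SD, the standard error of the log-scale mean is proportional to 1/√n, so the ratio to the full cohort is √(6/n).
- One withdrawal: n = 5, a loss of 1/6 = 17% of subjects; √(6/5) = 1.095, so +10%.
- Two withdrawals: n = 4; √(6/4) = 1.225, so +22%.

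**Step 4. Which analyses are touched.**
- Day 1 Cmax, tmax, AUC(0-8), Day 1 concentrations and Days 2 to 6 troughs: yes.
- Day 7 parameters: no, because the subject has no final-dose profile under any rule.
- Accumulation ratio: no, because it needs AUC(0-8) after the last dose.
- Power model: no, because SAP 10.6.3 uses last-dose Day 7 data.
- Safety: no, because the Safety Population has no completion condition.

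**Step 5. Does any passage keep the data?**
- The affected-treatment-period rule in SAP 9 is triggered by a significant protocol deviation, and withdrawal is not named as one. Nor does it separate Day 1 from Day 7, because protocol 7.3 places both in one treatment period.
- Protocol 5.3.3 says that withdrawn subjects' data are evaluated for PK, but it does not say that they enter summary statistics.
- SAP 10.5.1, 10.5.4 and 10.6.2 allow for incomplete data, but they do not alter who belongs to the population.
- The by-cohort sentence in SAP 10.6.3 covers all data, but SAP 10.1 limits summaries to the relevant population.

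The passages pull in different directions, and none settles the matter.

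**The case against.** The strict reading is not the only one. The clause does not say that all measurements must be completed, and it names no day. Its examples are data-quality failures: early vomiting, processing errors and inaccurate dosing. It can therefore be read as asking that the measurements taken be free of distortion. A rule of at least one dose adds little if the whole course must be sampled, and partial exclusion is largely redundant if membership is all or nothing. SAP 10.1 also does not name a population for each table; that detail is left to the table shells, which are a separate document. These arguments stand. They make profile-level handling the likely intention, but they do not write it into the membership rule.

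A reader might also infer more than the documents support:
- *That dose escalation review loses the data.* SMC and FDA review is not stated to be limited to the PK population.
- *That a halt empties a cohort.* The Day 1 n falls from 6 to 0 (6 × 11 = 66 samples unsummarised) only if all six active subjects have complete Day 1 profiles and are still on treatment, dosing stops before the final dose and never resumes, and the strict reading is applied. That is a worst case. SAP 6 refers a halt to the SMC, which also considers replacement at the same dose level.
- *That a missed Day 10 sample excludes a subject.* Protocol 7.3.4 makes that sample optional. Table 6 is a blood-volume budget that would naturally count it. SAP 6 omits the word optional, which is a separate wording mismatch.
- *That the summaries would be biased in a known direction.* Nothing in the documents fixes a direction.

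**Conclusion.** The point holds as an unreconciled conflict. Taken at its word, the completion condition in SAP 9 and protocol 11.4.1, applied through SAP 10.1, discards valid Day 1 and trough data of a subject withdrawn before the final Day 7 dose. Protocol 5.3.3, SAP 10.6.3 and the parameter-level rules suggest that those data should be used. It is not shown that the sponsor intends the exclusion.

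The size is modest: n goes from 6 to 5 in a cohort's Day 1 summaries for one withdrawal, with the standard error of the log mean up 10%, or up 22% for two. This assumes the same SD and that the PK population governs the Day 1 and trough tables. The SAP plans no confidence interval for Day 1, so the figures only illustrate precision. The current text gives no withdrawal or halt rate, so no probability is claimed. The change should still be made, because it costs almost nothing and removes a choice that would otherwise be made with concentrations in hand.

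**What to change.** In SAP 9 and protocol 11.4.1:
- Replace the completion condition. The PK population becomes subjects who received at least one dose of UV-4B and have at least one evaluable post-dose concentration or PK parameter.
- Keep the exclusion for deviations or events that materially affect PK, but apply it by profile or sampling day: Day 1, each trough, Day 7. Let SAP 10.5.3 and 10.5.4 govern only half-life and AUC, since they set no criteria for Cmax, tmax or troughs.
- State that valid data collected before withdrawal, or before a halt in dosing, stay in the summaries, with n shown for each.

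As a separate minor edit, align SAP 6 with protocol 7.3.4 on the optional Day 10 sample, and state that its absence does not affect membership.

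The cost is wording only, with no new data or analyses. The downside is that n may differ between Day 1 and Day 7 summaries; SAP 10.1 already lists n among the summary statistics.
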